### Methodological approach

The study is a parallel group trial, with 1:1 procedure-stratified randomization between the Team Monitoring and Enhanced Feedback arms. The two groups will differ by how their self-reported symptom information is handled: Enhanced Feedback (system displays the patient's self-reported symptom data alongside expected norms for that procedure, and patient initiates care escalation) vs. Team Monitoring (the patient completes self-reported symptom assessment as per standard care at MSKCC; the clinical team contacts the patient if symptoms are above expected levels or appear to be worsening). Note: When patients report severe symptoms in either group, the care team will receive an alert and patients will also be instructed to immediately contact the clinical team. (Alerts to the clinical team can only be monitored during business hours, so all patients must seek care after hours in the current standard care fashion.) Our study design follows CONSORT and PCORI standards, including patient engagement, research methods, data integrity and

analysis (including stratification by surgical procedure), handling of missing data, and heterogeneity of treatment effect.

**Primary outcome:** The primary outcome for Aim 1, emergency department visits up to 30 days after ambulatory cancer surgery, is important to patients because emergency department visits are time-consuming and may increase anxiety and caregiver burden. It is relevant to health care systems and clinicians because such visits are inefficient and costly and may erode trust between the patient and provider.

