### Power calculation

Sample size and power calculations were based on the primary outcome, the difference in emergency department visits without admission, between the Enhanced Feedback and Team Monitoring arms. On the basis of current MSKCC data, we expect for every 1,000 eligible patients treated surgically at JRSC, 69 patients will make emergency department visits. We also estimate that of these 69 patients, 28 will require readmission, and hence 41 will have visits the emergency department unnecessarily. The majority of such unnecessary visits are related to concerns about symptoms, which might be avoided if patients have a better understanding of expected symptom severity. Using a traditional alpha of 5% and an event rate of 4.1% in the control group, the power to detect different relative risk reductions is given below for a total sample size of 2,750 patients.

Relative Risk Reduction	Power
33%	45%
40%	64%
50%	85%
67%	96%

The primary analysis will compare, between groups, the proportion of patients with at least 1 emergency department visit without admission within 30 days (SA1a) of surgery by logistic regression with randomization strata as covariates. A difference between proportions will be calculated along with a 95% CI by applying the odds ratio from the regression to the event rate in the control group. A similar statistical approach will be taken for the proportion of patients referred to pain management and unplanned clinic visits (SA1b). For nursing follow-up calls (SA1b), phone referrals (SA1b) and rates of adverse events (SA1b), we will use both a binary approach (e.g., at least 1 nursing call vs. no nursing call) and analysis of count data using negative binomial regression with randomization strata as covariates. For all binary endpoints, an event will be counted only if it occurs within 30 days of surgery.

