For the endpoints of patient engagement (SA2a) and caregiver burden (SA2c), we will use linear regression with randomization strata as covariates for each subscale separately. For all analyses, we will report an estimate of the difference between groups along with a 95% CI and a two-sided P value for the null hypothesis of no difference between groups. For the endpoint of patient anxiety (SA2b), as measured by the PRO-CTCAE, we will enter daily anxiety scores as a continuous outcome variable into a longitudinal mixed effects model with time, treatment, and treatment by time interaction as predictors and randomization strata as covariates. As all data are collected after randomization, both the treatment term and the treatment by time interaction term are valid indicators of a treatment effect. We hypothesize that initial anxiety will be similar between groups and will be related to immediate postoperative concerns. Subsequent anxiety may be related to emergent symptoms, whether they are considered worrying and how they are dealt with. Hence, we will treat the time by treatment interaction as the primary hypothesis for the purpose of establishing the treatment effect of enhanced feedback on patient anxiety.

In exploratory analysis, the mean of each PRO-CTCAE item (0–4 scale) will be compared between groups during the 10-day post-surgery daily reporting period using the same longitudinal mixed effects model described above for anxiety with time, treatment, and treatment by time interaction as predictors and randomization strata as covariates. All available data will be used in these models. This likelihood-based approach to the analysis of longitudinal PRO data provides valid estimates of intervention effects in the presence of ignorable missing data and is known to be robust to nonignorable missing data if covariates and previous values of the outcome explain much of the missingness.

Supplemental analysis will also employ longitudinal mixed ordinal logistic models to compare ordinal PRO-CTCAE scores between arms.

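### The 95% CI for the primary risk difference ignores sampling error in the control rate and covers only about 84% of the time at a 50% relative reduction

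*Combined protocol and SAP*

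**What the plan says.** Section 11.0, under Power calculation, compares the proportion of patients with at least one emergency department visit without admission within 30 days "by logistic regression with randomization strata as covariates". For the absolute effect it then states: "A difference between proportions will be calculated along with a 95% CI by applying the odds ratio from the regression to the event rate" (the control arm's rate). The text that follows promises, for all analyses, a between-group difference, a 95% CI and "a two-sided P value for the null hypothesis of no difference between groups".

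Nowhere in section 11.0 is there a delta-method, bootstrap, standardisation or other step that brings the uncertainty of the control rate into the interval. The missing-data and sensitivity subsections do not touch the point. The plan takes a similar approach to pain management referrals and unplanned clinic visits.

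**The concern.** The control rate is not known. It is estimated from the same trial and appears twice: as the baseline to which the odds ratio is applied, and inside the odds ratio itself. When the observed control rate is high by chance, the estimated odds ratio is low by chance, so the two are negatively correlated. Holding the rate fixed drops both its own error and this correlation.

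Sections 4.2 and 9.0 justify the endpoint by its relevance to patients, clinicians and health systems. The absolute difference in visits is the figure those readers will use. If the trial's hypothesis is true, that figure would be published with error bars that are too tight.

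**Working it through.** **Inputs, all from the plan**
- Control rate p0: "an event rate of 4.1% in the control group" (section 11.0).
- Sample size: "for a total sample size of 2,750 patients" (section 11.0), "with 1:1 procedure-stratified randomization between the Team Monitoring and Enhanced Feedback arms" (section 4.2), so n = 2,750 / 2 = 1,375 per arm.
- Alpha 5%, two-sided (section 11.0).
- Effects: the relative risk reductions in the power table. At 50%, p1 = 0.041 × 0.5 = 0.0205.
- Expected events at 50%: 1,375 × 0.041 ≈ 56 in the control group and 1,375 × 0.0205 ≈ 28 in the Enhanced Feedback group.

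**The plan's own figure first.** A two-proportion power calculation with continuity correction gives 85.2% at a 50% reduction (plan: 85%), 63.6% at 40% (plan: 64%) and 45.5% at 33% (plan: 45%). The inputs are therefore the plan's. The 67% row computes to about 99% against a stated 96%; nothing below depends on that power figure.

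**Why the interval is wrong.** Write q = 1 − p.
- With p0 held fixed, the treated risk changes with the log odds ratio at rate p1q1. The variance used is (p1q1)² × [1/(n·p0q0) + 1/(n·p1q1)].
- The true variance of the difference is (p0q0 + p1q1)/n.
- The first divided by the second simplifies to **p1q1 / (p0q0)**. This is 1 under no effect, below 1 under benefit and above 1 under harm.
- At 50%: p0q0 = 0.041 × 0.959 = 0.03932 and p1q1 = 0.0205 × 0.9795 = 0.02008. The ratio is 0.511, and its square root is 0.715.
- Approximate coverage = 2Φ(1.96 × 0.715) − 1 = 83.9%.

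**Worked example at the expected rates**
- Odds ratio = (0.0205/0.9795) / (0.041/0.959) = 0.490.
- SE of log OR = √(1/54.06 + 1/27.61) = 0.234, so the 95% limits are 0.310 to 0.774.
- Applying those limits to a control rate of 4.1% gives a risk difference of −2.05 points with CI **−2.79 to −0.90**.
- With both arms' variance, SE = √[(0.03932 + 0.02008)/1,375] = 0.657 points, giving CI **−3.34 to −0.76**.

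**Exact coverage.** Both binomials were enumerated with n = 1,375 per arm. The as-written interval is expit(logit(p̂0) + log OR ± 1.96·SE) − p̂0.

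| True effect | As written | Both arms' variance (Wald) |
|---|---|---|
| None | 95.2% | 95.0% |
| 20% reduction | 92.2% | 95.0% |
| 33% reduction | 89.3% | 95.0% |
| 40% reduction | 87.2% | 95.0% |
| 50% reduction | 83.5% | 94.9% |
| 67% reduction | 74.2% | 94.9% |
| 50% increase | 98.3% | 95.0% |

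At 50%, mean width is 1.90 points as written against 2.57, so the interval is about 26% too narrow (1 − 1.90/2.57). It lies wholly on the side of too much benefit in 6.2% of trials and wholly on the side of too little in 10.3%, against 2.5% each.

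**With the planned strata.** Section 12.3 lists 3 + 4 + 4 + 2 = 13 strata. The plan gives neither stratum sizes nor stratum event rates, so shares were assumed and the between-stratum SD of the log odds was set at 0, 0.5 and 0.8. With 4,000 simulated trials per setting and a stratum-adjusted logistic model, as-written coverage at 50% was 82.7% to 84.5%. Standardisation from the same model with a delta-method variance gave 94.9% to 95.3%.

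**The case against.** The strongest reply is that the plan never says the control rate is held fixed. An analyst could put a delta-method or bootstrap interval around the same transformed estimate and stay within the wording. That is possible, but the sentence says the interval itself comes from applying the odds ratio to the control rate and names no other variance source. The literal reading is the natural one. If the rate were a fixed constant equal to the true rate, coverage would be about 95%. However, the text refers to the event rate in the control group, which is naturally the trial's observed rate.

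Three further points stand and limit the concern:
- The primary test is untouched. The as-written interval excludes 0 exactly when the odds ratio interval excludes 1.
- The plan names no single design effect. The 50% row is simply the smallest listed reduction with at least 80% power, and the shortfall is smaller at smaller effects. In the worked example the limit nearest zero moves by only 0.14 points (−0.90 to −0.76), with more of the change at the far limit.
- Beyond the primary endpoint, the construction is carried over expressly only to pain management referrals and unplanned clinic visits. For nursing calls, phone referrals and adverse events the plan mentions a binary approach without saying how a risk difference would be obtained. No event rates are given for secondary endpoints, so no coverage figure can be attached to them.

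**Conclusion.** The concern holds. Taken as written, the interval labelled 95% for the primary absolute effect covers about 84% of the time at a 50% relative reduction (83.9% by the delta method, 83.5% exactly, 82.7% to 84.5% with strata). It is already below 90% at 33%, the smallest effect in the power table. Coverage is nominal only when there is no effect.

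This rests on a 4.1% control rate, 1,375 patients per arm, and the reading that the odds ratio limits are applied to the observed control rate. The stratified range also rests on assumed stratum shares and rate spreads. The trial's yes-or-no conclusion is not at risk. The stated precision of its main effect estimate is, and it should be corrected before analysis.

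**What to change.** Replace the sentence in section 11.0 with one to this effect: *The adjusted risk difference will be obtained by marginal standardisation. Each patient's risk will be predicted under each arm from the planned logistic model and averaged over all randomised patients in the analysis. The 95% CI will come from the delta method or a bootstrap that carries the uncertainty of both arms.* State that the same method serves every binary endpoint, and that the odds ratio P value remains the primary test. State also that strata with no events in either arm stay in the average with a predicted risk of zero, as was done in the check above.

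The cost is a short SAP edit and a standard post-estimation command. Design, sample size and data collection do not change. When Enhanced Feedback works, the reported interval will be wider (by about 35% at a 50% reduction: 2.57/1.90 = 1.35). In rare borderline cases it may disagree with the odds ratio P value, so the SAP should say that the P value governs the test.

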**Secondary outcomes:**

**SA1:** We will evaluate symptom-triggered interventions (nursing follow-up calls, unplanned clinic visits and phone referral to clinic, pain management referrals, and adverse event detection) and rates of adverse events up to 30 days after ambulatory cancer surgery. We will also evaluate the number of readmissions up to 30 days. Adverse events will be defined according to the nomenclature established in the MSKCC Surgical Secondary Events Grading System.

**SA2:** We will evaluate patient engagement, patient anxiety, and caregiver burden with the experience of care using validated PROs measures and qualitative interviews.

- Patient engagement will be evaluated preoperatively and at 2 weeks and 2 months postoperatively using the Patient Activation Measure (description below).
- Patient anxiety will be measured on a daily basis for 10 days following surgery using three PRO-CTCAE Anxiety questions.
- Caregiver burden will be evaluated at 2 weeks and 2 months postoperatively among consenting caregivers using the Caregiver Reaction Assessment (description below). Each participating patient will be asked to identify a caregiver, who will then be invited to participate.
- Patient engagement and caregiver burden will also be evaluated using qualitative interviews, with a sample of each of the randomized cohorts, as described below.

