### Study outcomes

	Aims	Measure	Data Source(s)	Assessment Time Point
Patient-Centered Outcomes	SA1			
Emergency Department Visits	SA1a	UCC visit at MSKCC	MSK institutional database	Up to 30 days after surgery
	SA1a	Emergency department visit outside MSKCC	Patient self-reporting via Patient Portal and corroborating phone call to patient by study team; MSK institutional database	Up to 30 days after surgery
Readmissions	SA1a	Readmission to MSK	MSK institutional database	Up to 30 days after surgery
	SA1a	Admission outside MSK	Patient self-reporting via Patient Portal and corroborating phone call to patient by study team; MSK institutional database	Up to 30 days after surgery
Symptom-Triggered Interventions	SA1b	Nurse calls due to alerts	Documented in EMR via clinical information system	Up to 30 days after surgery
	SA1b	Unplanned clinic visits and phone referral to clinic	Documented in EMR	Up to 30 days after surgery

	SA1b	Pain management referrals	Documented in EMR	Up to 30 days after surgery
	SA1b	Adverse event detection	EMR and MSKCC Surgical Secondary Events Database	Up to 30 days after surgery
Patient and Caregiver Health Care Experience	SA2			
Patient Engagement	SA2a	The Patient Activation Measure 	Patient self-report	Preoperatively (day of consent-POD1), 2 weeks (+7/-3 days), 60 (+/- 14) days after surgery
	SA2a	Qualitative data	Semistructured patient interviews	30 (+/- 10) days after surgery
Patient Anxiety	SA2b	PRO-CTCAE Anxiety Items	Patient self-report via symptom monitoring module in the Patient Portal	Daily for 10 days after surgery
Caregiver Burden	SA2c	Caregiver Reaction Assessment 	Caregiver self-report	2 weeks (+7/-3 days), 60 (+/- 14) days after surgery
	SA2c	Qualitative data	Semistructured caregiver interviews	30 (+/- 10) days after surgery

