### Patient and caregiver health care experience

**The Patient Activation Measure.** The Patient Activation Measure is a validated PRO measure developed to evaluate the engagement of patients in their care. The development process included conceptual definition and item generation through patient focus groups, literature review, and expert panel consensus. Psychometric evaluation of the scales was performed using Rasch psychometric methods, and further validation was completed in a large national sample. This measure includes items querying patients about their confidence (self-efficacy) and knowledge to take action specific to their health. Items include *“I am confident I can tell when I need to get medical care”* and *“I am confident I can take actions that will prevent or minimize symptoms or problems.”* This PRO measure was selected because it evaluates a key concept of interest in our study, was rigorously developed with qualitative and quantitative methods, and has strong psychometric properties. PAM yields only a total score that will be used in the analysis.

**The Caregiver Reaction Assessment.** The Caregiver Reaction Assessment is a validated instrument designed to assess the impact of caregiving on disrupted schedules, self-esteem, and financial and health problems. The Caregiver Reaction Assessment assesses specific aspects of the caregiving situation, including both negative and positive dimensions of caregiving reactions. The Caregiver Reaction Assessment (CRA) consists of 5 subscales, 4 of which are negative and 1 positive. The negative subscales have higher scores indicating higher level of burden, rated from 1 (strongly disagree) to 5 (strongly agree). The four negative subscales are: Impact on

Schedule (5 items), Impact on Health (4 items), Lack of Family Support (5 items) and Impact on Finances (3 items). The positive subscale, Caregiver's Self Esteem (7 items), has lower scores indicating higher levels of burden rated from 1 to (strongly disagree) to 5 (strongly agree).

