## **7.0 ASSESSMENT/EVALUATION PLAN**

The Recovery Tracker will be completed by all patients for up to 30 days following their surgery. Patients will be sent the Patient Activation Measure (PAM) through the MyMSK Patient Portal (see Appendices A and H). In the event the electronic PAM survey is not available, a hardcopy version will be provided to the patient to complete.

Caregivers will be asked to provide their email and will be sent the Caregiver Reaction Questionnaire and a brief demographic questionnaire through REDCap (see Appendices B, C, and H). In the event the electronic survey is not available, a hardcopy questionnaire will be provided to the caregiver to complete.

	# of Items	Pre-Op (day of consent - POD1)	POD 1-10	POD14 (+7/-3 days)	POD30 (+/-10 days)	POD60 (+/- 14 days)
Patient						
Recovery Tracker (including PRO-CTCAE symptoms and anxiety items, and additional questions)	20		Daily		Available to complete if desired (POD11-30)	
Emergency Department Visits					X	
Readmission					X	
Adverse Events					X	
Patient Activation Measure	10	X		X		X
Patient Interviews					X	
Caregiver						
Caregiver Reaction Assessment	24			X		X
Caregiver Interviews					X	

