### **Approach to missing data for questionnaire items**

Baseline characteristics between those with and those without missing data will also be compared to assess for bias. The rate of missing data is expected to be low. The main threat to data completion involves the caregiver and patient questionnaires obtained at 2 weeks and 2 months, respectively. In addition to automated electronic reminders, a research assistant will follow up with patients who have missing data. Patients from whom no data are obtained will be classified as “unable to contact,” “too busy/uninterested,” or “intervention related” (e.g., a patient who declines to complete the questionnaires because of an experience earlier in the trial). Patterns of missing data will be compared by treatment arm. In the unlikely event that the rate of missing data is more than 5%, we will impute missing data using multiple imputation by chained equations, with results combined using Rubin’s rules. The principle assumption of such a method is that the data are “missing at random” or “missing completely at random.” It seems at least possible that any missingness will be nonignorable on the grounds that a patient with a poor level of patient activation will be less likely to complete surveys. We will therefore repeat multiple imputation, except instead of missing activation measures being sampled from a distribution centered on the mean they will be sampled from the 25th and, alternatively, 10th percentiles. A similar approach will be taken for the caregiver measure, for comparable reasons.

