### **Heterogeneity of treatment effect**

It is possible that the effects of Enhanced Feedback vary predictably between patients. Although it is common to assess computer literacy as an effect modifier in trials of patient-facing software, we believe that this is inappropriate for the current proposal. This is because both groups will interface with the software, and the difference between the two groups is not highly software dependent. It does, however, seem plausible that patient willingness to make proactive decisions about their postoperative care in the light of data about expected symptoms would be mediated by age, educational status, and the type of procedure they undergo. We will therefore repeat all analyses including

interaction terms between allocation and age, education, and procedure. Educational status is obtained routinely at baseline for all MSKCC surgery patients and will be coded as a binary variable: education after high school/high school only. The models will be of the following form (with a linear case being shown for the sake of simplicity):

$$y = \beta_1 \text{ Allocation} + \beta_2 \text{ Age} + \beta_3 \text{ Allocation} \times \text{Age} + \beta(\text{Randomization stratum}) + c$$

Allocation is coded 1 for Enhanced Feedback and 0 otherwise; randomization stratum is a categorical variable. A similar model will be used for educational status and procedure type. We have no particular reason to believe that response to Enhanced Feedback would vary by race and ethnicity, but as a check to ensure that our approach does not inadvertently discriminate, we will conduct exploratory analyses of race and ethnicity using the structure of the model described above.

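### The patient engagement analysis (SA2a) gives the preoperative PAM no role; adjusting for it would narrow the confidence interval at almost no cost

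*Combined protocol and SAP*

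**What the plan says.** Under Secondary outcomes in section 4.2: "Patient engagement will be evaluated preoperatively and at 2 weeks and 2 months postoperatively using the Patient Activation Measure". The Study outcomes table sets the windows as "Preoperatively (day of consent-POD1), 2 weeks (+7/-3 days), 60 (+/- 14) days after surgery", and the schedule in section 7.0 labels the first one "Pre-Op (day of consent - POD1". Section 15.1 (Patients) also counts three occasions for the patient survey. Under Patient and caregiver health care experience the score is fixed: "PAM yields only a total score that will be used in the analysis".

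The SA2a analysis is one sentence in section 11.0, shared with caregiver burden: "For the endpoints of patient engagement (SA2a) and caregiver burden (SA2c), we will use linear regression with randomization strata as covariates". It goes on to say that each subscale is modelled separately, which fits the Caregiver Reaction Assessment (CRA) but not an instrument with only a total score.

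Three other places could have given the preoperative PAM a role, and none does:

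- **Missing data for questionnaire items:** "In the unlikely event that the rate of missing data is more than 5%, we will impute missing data using multiple imputation". No imputation predictors are listed.
- **Heterogeneity of treatment effect:** "The models will be of the following form (with a linear case being shown for the sake of simplicity". The equation has allocation, age, their interaction and the stratum, and no baseline outcome.
- **Data sources:** age, sex, race and comorbidities are named as covariates. PAM is not.

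Section 12.3 defines the strata by surgical procedure, so they do not stand in for baseline activation. It also says that the trial is unblinded and that patients are randomized no more than a week from the surgical visit.

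**The concern.** A preoperative measurement of the outcome is usually its strongest predictor. Collecting it from every patient and then leaving it out of the model gives up precision that costs nothing more to obtain. Engagement is the mechanism through which the trial expects Enhanced Feedback to work, so a sharper estimate has value even for a secondary endpoint.

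The text also leaves a choice open. The outcome could be the 2-week score, the 60-day score or a change from baseline, and baseline could be a covariate or not. These options give different interval widths. In an unblinded trial the choice should be written down before the data are analysed.

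A third gap affects any remedy. The preoperative window runs to the day after surgery, and the order of PAM completion and randomization is not stated. Some scores labelled preoperative may therefore come after the patient knows the allocation. Adjusting for every score in the window without checking would risk adjusting for a post-randomization value.

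SA2c is not part of this point, because the outcomes table and the schedule in section 7.0 place the CRA only after surgery.

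**Working it through.** The plan states no power, SD or effect size for SA2a, so there is no figure of its own to reproduce.

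**Inputs from the documents.** 2,750 patients (section 1.0) randomized 1:1 (section 4.2), so 1,375 per arm; two-sided P values and 95% intervals (section 11.0).

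**Assumptions.** Everyone has a follow-up score. Results are in units of the follow-up SD within strata. The correlation r between baseline and follow-up PAM within strata is 0.3, 0.5 or 0.7. The share f of patients with a PAM completed before randomization is 1, 0.8, 0.5 or 0.2.

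**Strata-only, as written.** SE = √(2/1375) = 0.0381 SD. The 95% half-width is 1.96 × 0.0381 = 0.0748 SD. The difference detectable with 80% power is (1.960 + 0.842) × 0.0381 = 0.107 SD.

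**Baseline PAM as covariate.** Among patients with a usable baseline the residual variance falls to 1 − r². Among the rest, kept through a missing-baseline indicator, it stays at 1. The average is f(1 − r²) + (1 − f) = 1 − f·r², so the interval is multiplied by √(1 − f·r²).

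| Share usable f | r = 0.3 | r = 0.5 | r = 0.7 |
|---|---|---|---|
| 1.0 | 0.954 (0.0713 SD) | 0.866 (0.0647 SD) | 0.714 (0.0534 SD) |
| 0.8 | 0.963 (0.0720 SD) | 0.894 (0.0669 SD) | 0.780 (0.0583 SD) |
| 0.5 | 0.977 (0.0730 SD) | 0.935 (0.0699 SD) | 0.869 (0.0650 SD) |
| 0.2 | 0.991 (0.0741 SD) | 0.975 (0.0729 SD) | 0.950 (0.0710 SD) |

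Each cell gives the width multiplier and, in brackets, the 95% half-width.

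With complete baselines the detectable difference falls from 0.107 SD to 0.102, 0.093 or 0.076 SD. In patient numbers, the adjusted model would match the strata-only precision with 2,750 × (1 − r²) = 2,502, 2,062 or 1,402 patients. For an illustrative true difference of 0.10 SD, power rises from 74.6% to 78.5%, 85.7% or 95.7%.

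**If a change score was meant (f = 1).** Its variance is 2(1 − r), so the width relative to strata-only is √(2(1 − r)) = 1.183, 1.000 or 0.775: 18% wider, equal or 23% narrower. The covariate model relative to the change score is √((1 + r)/2) = 0.806, 0.866 or 0.922: 19%, 13% or 8% narrower.

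**Check of the missing-baseline indicator.** Trials were simulated with 2,750 patients, the 13 procedure strata and a true effect of 0.1 SD, 1,500 per setting.

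- With baselines missing completely at random, the mean SE was 3.6%, 10.6% and 22.0% smaller than strata-only at f = 0.8, and 2.2%, 6.4% and 13.1% smaller at f = 0.5. Bias was at most 0.002 SD and coverage of the 95% interval was 94–96%.
- The missing-data section worries that "a patient with a poor level of patient activation will be less likely to complete surveys". With baselines missing more often at low activation (logit slope 0.7 per SD), the SE was 3.6%, 10.5% and 21.9% smaller at 78% usable, and 2.5%, 7.1% and 14.5% smaller at 50% usable. Bias was again at most 0.002 SD, and coverage was 95–96%.

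The indicator is safe here because neither a pre-randomization score nor its absence can depend on an allocation that has not yet been made.

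**The case against.** The strongest reply is that nothing is broken. The planned comparison is unbiased, its interval already allows for chance baseline imbalance, the primary endpoint is untouched and no SA2a power target is missed. With 1,375 per arm the detectable difference is already 0.107 SD, and the documents give no PAM effect size to show that 0.093 SD would matter. All of that is true. It makes this an efficiency and specification point. It is no reason to leave out a score that is already collected.

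The second reply concerns the size of the gain. Section 6.1 allows consent on the day of surgery, so few PAMs may precede randomization. At 20% usable the interval narrows by only 0.9%, 2.5% or 5.0%. This stands as a limit on the benefit, but the adjusted model still does no harm there. It can also be said that a PAM completed after randomization but before the day-1 survey precedes any symptom feedback. Because the trial is unblinded, the pre-randomization rule is the safer one.

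Third, the plan may have intended a change score, in which case strata-only is not the right comparator. That is possible, but the text does not say so, and with complete baselines a covariate is more precise than a change score at every r shown.

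Two practical points also stand. Section 7.0 allows paper PAMs, and the documents do not say that their completion times are recorded. Section 15.1 (Caregivers) gives three survey occasions against two elsewhere. That mismatch needs separate reconciliation and does not affect SA2a.

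**Conclusion.** The concern holds. The plan schedules a baseline measurement of the SA2a outcome for every patient and states no use for it, and it does not say which follow-up score is analysed. The consequence is lost precision and an open choice on a secondary endpoint, not bias. The gain from adjustment is about 5–29% in interval width with complete baselines, 4–22% with 80% usable, 2–13% with 50% and 1–5% with 20%, for r from 0.3 to 0.7. That the PAM has no stated role is certain from the text. The size of the gain rests on r and on the share of PAMs completed before randomization, and the documents give neither. The change should be made because it is cheap and cannot damage the comparison.

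**What to change.** In section 11.0, separate SA2a from SA2c and specify:

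- **Model:** linear regression of the PAM total score at 2 weeks and, separately, at 60 days on allocation, randomization strata and baseline PAM, reporting the adjusted difference with its 95% CI. If one time is to lead, say which.
- **Baseline:** only a PAM completed before randomization counts. Patients without one stay in the model, with baseline set to a constant and a missing-baseline indicator added. A paper form with no recorded completion time is treated as missing.
- **Missing follow-up scores:** keep the existing 5% imputation rule, name baseline PAM as a predictor, and say how it enters the low-percentile sensitivity imputations.
- **Sensitivity analysis:** the strata-only regression as now written.

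Leave the SA2c model unchanged.

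The cost is SAP wording, a comparison of each PAM completion time with the randomization time, and two extra regression terms in up to 2,750 patients. No new questionnaire or visit is needed. The downside is a smaller gain if many PAMs are completed after randomization.
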